## 8 ADVERSE EVENTS

An adverse experience is defined as an unfavorable and unexpected change in the structure, function, or chemistry of the body, transiently associated with the use of the study product, whether or not related to the use of the drug. Any worsening (i.e., any adverse change clinically significant in terms of frequency or severity) of a pre-existing condition that is transiently associated with use of the study product is also an adverse experience.

Adverse events will be documented from the time of enrollment (i.e., at the time of signing the informed consent form) through the last scheduled contact as per the protocol, i.e., the date of the last visit/contact (may be a phone call, for example, in case the participant withdraws from the study).

### Definition of Serious Adverse Event (SAE)

A SAE is any medical incidence that, at any dose:

- Results in death; or
- Is life-threatening (puts the subject, from the investigator's perspective, in an immediate risk of death due to the experience that took place. This includes direct life-threatening experiences but not those that could potentially put life at risk), or
- Requires or prolongs hospitalization of the patient (hospitalization is defined as an admission, regardless of length of stay, even if hospitalization is a precautionary measure in order to continuously monitor the patient). If this hospitalization is due to a non-worsening pre-existing condition, it is not to be considered as a serious adverse experience.

- Results in persistent or significant inability/disability (major impairment to the ability to perform daily life functions); or
- Is an abnormal congenital defect or birth defect
- Is considered a clinically significant medical event

A scheduled hospital admission, for example, for elective surgery, is not considered a SAE if documented at the time of enrollment.

All patients randomized in the study are pregnant women, therefore, hospitalizations related to scheduled parturitions/full term deliveries will not be considered as adverse events nor as serious or relevant adverse events.

#### **Definition of Adverse Event of Special Interest**

Adverse events of special interest are adverse events considered important for assessment of the safety profile regardless of seriousness, expectancy, and severity classification.

Preterm birth is the birth of a fetus before 37 weeks of pregnancy. Preterm birth will be considered an event of special interest and should consequently be reported within 24 hours.

#### **Expected Adverse Events**

Expected Adverse Events will be evaluated by the Sponsor.

An unexpected adverse event is one where the nature or severity is not consistent with the information contained in the relevant source document, i.e. the Investigator Brochure.

In addition, reports that add significant information about the specificity or seriousness of a known, already documented adverse reaction are unexpected adverse events. For example, an adverse event more specific or more serious than expected would be considered "unexpected."

#### **Definition of Adverse Drug Reactions**

An Adverse Drug Reaction is any harmful and undesirable response to an Investigational Medicinal Product (IMP) or drug, regardless of the dose administered.

All adverse events reported by subjects spontaneously at any time point should also be documented.

All adverse events should be documented in the CRF with the following information according to the case:

- Description (adverse events reported within the term)
- Start date
- End date or continuation
- Whether the adverse event was serious
- Severity

- Outcome
- Mitigation actions
- Causal relationship with the IMP
- Definition of severity

The clinical severity of an adverse event will be classified as:

Mild:	The signs and symptoms can be easily tolerated. Symptoms may be ignored and disappear when the subject is distracted.
Moderate	Symptoms cause discomfort but are tolerable, not ignorable, impairing concentration ability
Severe	Symptoms affecting daily life activities.

For adverse events where intensity changes over time, the maximum intensity observed throughout the adverse event will be documented.

Adverse events that occur during the enrollment period, but prior to the first administration of the IMP and worsen during or after administration of the IMP will be documented as new adverse events.

**Definition of outcomes at the time of the last observation of the adverse event**

The outcome at the time of the last observation will be classified as:

- Recovered/Resolved
- Recovering/Resolving
- Not recovered/Not resolved
- Recovered/Resolved with sequelae
- Fatal
- Unknown (unknown should only be used if, at the time of the subject’s last visit in a trial, the outcome of the adverse event is unknown to the investigator, for example, because the subject was a lost to follow-up)

**Definition of the mitigation actions:**

• None:	No mitigation actions have been provided
• Start of new medication:	Start of new medication or change in the dosage or route of administration of a drug due to an adverse event (which will be listed before/concomitantly with the medication sheet) that is used as a mitigation action.
• Interruption of the study:	Discontinuation of the subject participation in the study was required due to an adverse event.
• Other:	All other mitigation actions, e.g., physical therapy, surgery.

With the exception of “none”, multiple mitigation actions can be taken for an adverse event.

**Classification of causality:**

The causal relationship of an adverse event to the investigational product will be classified according to terminology as follows. The proposed criteria for each term are to be considered and not exhaustive and neither are required to be entirely fulfilled for choosing the respective term:

Terms for classification of causality	Criteria for choosing causality classification terms
Conditional/Unclassified	Additional data for proper evaluation are under examination.
Not Evaluable/Not	Assessment of available data may not be performed because the information is insufficient or contradictory, and may not be
Classifiable:	supplemented or verified.
Unrelated:	Data with sufficient evidence to accept that there is no causal relationship with the administration of the IMP (i.e., there is no time relationship with the administration of the investigational product or another cause has been proved).
Not possible:	Data without sufficient evidence to accept that there is no causal relationship to the administration of the IMP, though neither with evidence or argument to suggest a causal relationship (e.g., the temporal relationship with the administration of the investigational product makes a causal relationship unlikely and other drugs, chemicals, or underlying disease[s] provide plausible explanations).
Possible:	Data or a foundation with limited evidence suggesting a causal relationship (e.g. existence of a reasonable time sequence with the administration of the drug, but the adverse event could also be explained by concurrent disease[s] or other drugs or chemicals. Information regarding drug abstinence may not exist or be unclear).
Probable/Possible	Data or a foundation of enough evidence to suggest a causal relationship (e.g. existence of a reasonable time sequence with administration of the drug, the adverse event is unlikely to be attributed to concurrent disease[s] or other drugs or chemicals, and the response regarding dechallenge is clinically reasonable).
Certain	Data with evidence of a causal relationship (i.e., a clinical event, including alterations in laboratory tests, occurs under a plausible relationship with the time of administration of the drug, and simultaneous disease or other drugs or chemical substances may not explain it. Response to drug dechallenge should be well-defined and clinically plausible, using a successful rechallenge procedure where appropriate).

**Follow-up of subjects with an adverse event**

Follow-up on any clinically relevant, laboratory abnormality, or vital signs result adverse event will be performed until a satisfactory solution or stabilization is reached, or the clinical evaluation indicates that an additional evaluation is not warranted.

### **Reporting serious adverse events**

Any serious adverse event (SAE) regardless of cause, occurring to any woman admitted into the study, must be notified by the Principal Investigator within 24 hours to **[contact]**, and to the respective Institutional Review Boards. These reports should include all supporting documentation available (with the name of the subject crossed out) for each event, the summary of the hospital discharge.

The Technical Director of Laboratorios Andrómico S.A., [name] [REDACTED] will communicate the SAE to the local health regulatory authorities. Every SAE must be followed until it is completely characterized. This report must be sent earlier than 2 days after the study staff were notified of the event.

The Principal Investigator must submit a report called a Security Report Form (SRF), which includes a description of the event, the therapy initiated, and the testing procedures. The following information must be reported with the first report of a SAE:

- Study identification
- Subject identification
- Subject's date of birth (if available) or age (at the onset of the adverse event)
- Gender of the subject
- Indicate whether the condition was pre-existing or not, and if so, if it worsened
- First administration of the IMP (date and time, if available)
- Last administration of the IMP (date and time, if available)
- Brief description of the event, and mitigation arrangements taken, actions undertaken (does the adverse experience cause the study drug to be discontinued or interrupted?)
- Maximum intensity
- SAE severity criteria
- Outcome
- Concomitant medication at the onset of the event and if one of the concomitant medications is also suspected of having caused the event
- Relevant history/pre-existing medical condition
- The relationship with the study drug evaluated by the Investigator (determination of causality: Is the study drug the cause of the adverse experience?)

Any additional information relating to the adverse event until the termination of the trial or the final result shall be reported in the follow-up report without delay.

## **9 STATISTICS**

This project aims to conduct a randomized, open-label, controlled, clinical-exploratory phase II study evaluating the efficacy of a cerclage pessary containing one of 2 doses of sustained-release micronized progesterone for prevention of preterm birth, compared to the treatment method currently used by obstetrics-gynecology specialists, which comprises the administration of one daily capsule by vaginal route of 200 mg of progesterone. A total of

270 pregnant participants at risk of preterm birth will be enrolled, screened, and randomized to the 3 groups of treatment previously described. The number of patients listed ( $n = 270$ ) refers to the number of patients who effectively are enrolled and successfully complete the study. Therefore, an enrollment of at least 10% over that number (27 patients or more) should be considered due to the eventual withdrawal or early loss to follow-up of patients initially recruited.

As primary results, the proportions of spontaneous preterm delivery before gestation weeks 32 and 34 will be compared between the control group and the 2 groups with the pessaries containing different doses of progesterone. The risk of spontaneous preterm birth from the time of inclusion in the study through the gestation weeks 32 and 34 will be determined by a Kaplan-Meier analysis, where gestational age will be the time scale and spontaneous delivery will be the event; elective parturitions will be censored. For the purpose of this analysis, pregnancies will no longer be considered as high risk for the event if delivery occurs at the week of gestation 34 (34 0/7) or beyond.

As secondary outcomes, those qualitative variables in pregnant participants at risk of preterm birth will be evaluated, and the percentage distribution of acceptability responses or side effects recorded will be determined. For the quantitative variables (measurements of length and cervical angulation), the averages and standard deviations of the values found will be compared. Accordingly, each participant will work as her own control.

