## 2 RATIONALE

Nowadays, prematurity is a central issue both for obstetrics as well as for public health worldwide, as it is a highly incident clinical situation (affecting approximately 7% to 10% of births), and is involved in around 50 - 75% of neonatal morbidities and mortalities, mainly in neonates born before 32 weeks of gestation. Sequelae in premature neonates also impact on the increase of healthcare costs and infant mortality during the first year of life (1).

The rate of preterm births has not declined over the last 20 years, and in most developed countries it remains high despite advances in the knowledge about risk factors and mechanisms related to preterm births (2). Essentially, there are two reasons that explain the failure to reduce preterm births: first, the absence of a screening method effective for the identification of women at high risk for this event; and second, the lack of effective intervention to prevent this complication.

The most commonly adopted approach for identification of pregnancies at high risk for preterm birth has been the use of obstetrical history and mother's demographics.

In published screening studies where over 60,000 women with single pregnancies were included, the preterm birth rate by week 34 in England was 1.8%, very similar to that found in our country (1.3%). Preterm births were spontaneous in two-thirds of the cases (1.2% of the total), whereas one-third were iatrogenic. Only in 3% of cases, the patients had a history of preterm birth and this group accounted for 15% of the total number of spontaneous deliveries by week 34 only. This demonstrates that identification of patients at risk of delivery before week 34 based on obstetric history leaves most of these patients outside of the risk group, and therefore, not covered by preventive measures.

An effective method for prenatal screening to detect the risk of preterm birth is the measurement of the cervical length by ultrasound between gestation weeks 20 and 25. The risk of preterm birth both for single-fetus as well as for twin pregnancies is inversely related to the cervical length. Therefore, a woman with a cervical length (CL) between 1-10 mm has a risk of preterm birth of 44%, whereas a woman with a CL between 26-30 mm has a risk of 1.3%. The group with cervix measures of 1 to 15 mm corresponded to 28% of all spontaneous deliveries before week 34, and the group with a cervix measure of 16 to 25 mm corresponded to 21% (3).

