10. EFFICACY ANALYSIS

STATISTICAL HYPOTHESIS

Null Hypothesis:

There is no difference between the methods of cerclage pessaries with a sustained release of 6.3 and 7.7 g of progesterone (Treatments B and C, respectively) with respect to the control method (Treatment A) for at least 20 weeks.

Alternative Hypothesis:

There is a difference between the Control Method (Treatment A) with respect to the one of cerclage pessaries with a sustained release of 6.3 and 7.3 of progesterone for a period of 4 to 5 months.

“There is a difference between the methods of cerclage pessaries with a sustained release of 6.3 and 7.3 g of progesterone (Treatments B and C respectively) with respect to the Control Method (Treatment A) for a period of 4 to 5 months”.

PRIMARY ANALYSIS

The primary objective is to evaluate the efficacy of two cerclage pessaries with doses of 6.3 and 7.7 g of sustained release micronized progesterone with respect to the standard treatment of 200 mg of progesterone in capsules administered daily. The primary efficacy analysis will be assessed by comparing the proportions of spontaneous premature delivery after 32 weeks but before 34 weeks of gestation, as primary results, among treatments through the CMH test. Also, the odds ratio and 95% confidence interval will be estimated, considering Group A as the control to be compared with groups B and C. Secondly, the comparison of proportions between the groups C and A will be done with the intention to confirm the significant difference between the highest dose and the standard treatment. Afterwards, the same comparison of proportions will be done with treatment B in order to establish the difference between the group of a minor dose and the standard. Finally the comparison between treatment B and C will be done hoping to demonstrate there is a difference of superiority between B and C where C must be minor than B regarding the number of low-risk pregnancies. The transitivity between treatments will be established according to the results. This is expected to be as follows:

$$\textit{Treatment C} < \textit{Treatment B} < \textit{Treatment A}$$

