this is in terms of decrease of the proportion of pregnancies with premature risk. In this way it will be determined the effective response to progesterone in the cerclage pessary through the occurrence of spontaneous delivery after 32 weeks but before 34 weeks of gestation. The evaluation of the error type 1 will be with a value of 0.05 for the type of variable being used.

As part of the exploratory analysis for the efficacy of treatments, the risk of spontaneous premature birth from the moment of inclusion in the study until the weeks 32 and 34 of gestation, will be determined with the Kaplan-Meier analysis, where the gestational age is the timeline, spontaneous delivery will be the event and elective deliveries will be censored. A singleton pregnant subject between 16 and 24 weeks of gestation will be eligible to participate in the study when she meets one of the following two conditions:

- Cervical length between 10 to 25 mm and without risk factors
- Cervical length greater or equal to 10 mm and with pre-existing risk factors in the immediate preceding pregnancy characterized by:
 - premature delivery before the week 35 (with a viable fetus)
 - premature rupture of membrane prior to week 35 (with a viable fetus)

There are two ways to measure the gestational age which are the following:

- Gestational Age according to DLNM (weeks)
- Gestational Age according to Transvaginal Ultrasound (weeks)

The time of gestational age will be evaluated through log-rank tests among treatments. The null hypothesis is stated as the no treatment differences in the gestational ages.

Kaplan-Meier (product limit) estimates of the gestational age distribution will be calculated and their corresponding 95% confidence interval (CI) will be presented: 25th percentile, mean, median, and 75th percentile.

The analysis will be performed for the two measurements of gestational time, considering the Transvaginal ultrasound the one most accurate.

For the purposes of this analysis, pregnancies will no longer be considered of high risk in the event birth takes place in week 34 (34 0/7) of gestation or more.

SECONDARY ANALYSIS

For some of the secondary variables, subjects will be their own controls in the following variables to evaluate and the following analysis are proposed:

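### Censoring elective deliveries makes 1 minus Kaplan-Meier overstate the risk of spontaneous birth by weeks 32 and 34, probably by little, and some of the planned percentiles may never be reached

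*Protocol*

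**What the plan says.** Protocol section 9 sets the target as the risk of spontaneous preterm birth from inclusion through weeks 32 and 34, estimated by Kaplan-Meier on the gestational-age scale. Spontaneous delivery is the event, and "elective parturitions will be censored". SAP section 10 keeps the rule ("spontaneous delivery will be the event and elective deliveries will be censored") and introduces the analysis with the words "As part of the exploratory analysis for the efficacy of treatments". It adds a log-rank test and, with 95% confidence intervals, these summaries of gestational age: "25th percentile, mean, median, and 75th percentile". Neither document names a competing-risks method.

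The main comparison is of crude proportions. In protocol section 9, "the proportions of spontaneous preterm delivery before gestation weeks 32 and 34 will be compared". In SAP section 10 it is a CMH test "comparing the proportions of spontaneous premature delivery after 32 weeks but before 34 weeks of gestation".

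Both documents treat a pregnancy as no longer high risk for this analysis once birth occurs at 34 0/7 or later. Protocol section 5.4.5 closes cases at 36 6/7 weeks or at preterm birth. Neither document says at which gestational age events stop counting towards the percentiles.

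**The concern.** Kaplan-Meier treats a censored woman as someone who could still have the event later, at the same rate as the women still pregnant. After an elective delivery that is impossible. The curve therefore describes a hypothetical setting in which elective delivery does not occur, whereas the stated target is the risk in the trial as it runs. Protocol section 5.5 foresees elective deliveries, because it provides for pessary removal when early induction or elective cesarean is medically indicated.

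Two consequences follow. First, the report could show two different risks of spontaneous birth by week 34 for the same arm, one from the crude proportion and a higher one from the curve, with no explanation. Second, several promised summaries may come out as not estimable, because a percentile exists only where the curve reaches that level.

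**Working it through.** **Inputs.** The documents give no figure for the Kaplan-Meier analysis, so there is nothing to reproduce.

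- Size: 90 women per group (protocol section 9.1).
- Elective share: the only figure is in protocol section 2, "Preterm births were spontaneous in two-thirds of the cases (1.2% of the total), whereas one-third were iatrogenic". It gives elective to spontaneous = 0.5:1, but comes from general-population screening. A ratio of 0.1:1 is added as a low assumption.
- Spontaneous birth before 34 weeks in the trial arms: not stated. Assumed range 10% to 40%.

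**Step 1: size of the overstatement.** Let s and e be the actual proportions with spontaneous and elective birth before 34 weeks. With proportional cause-specific hazards and no other loss,

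1 − KM = 1 − (1 − s − e)^(s/(s+e)).

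For s = 0.20 and e = 0.10: 1 − 0.70^(2/3) = 1 − 0.788 = 0.212.

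The result depends on timing. If all elective births come first, the curve reads s/(1 − e), the upper bound. If all come last, there is no excess.

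| True risk s | e at 0.5:1 | 1 − KM | Excess (points) | Upper bound s/(1 − e) | 1 − KM at 0.1:1 |
|---|---|---|---|---|---|
| 10% | 5% | 10.3% | 0.3 | 10.5% | 10.1% |
| 20% | 10% | 21.2% | 1.2 | 22.2% | 20.2% |
| 30% | 15% | 32.9% | 2.9 | 35.3% | 30.5% |
| 40% | 20% | 45.7% | 5.7 | 50.0% | 41.0% |

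A simulation (90 women, entry uniform over weeks 16 to 24 with delayed entry, births uniform over weeks 24 to 34, 2000 runs) gave excesses of 0.3, 1.2, 2.9 and 5.8 points at 0.5:1.

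**Step 2: against sampling error.** At s = 15% and 0.5:1 the curve reads 1 − 0.775^(2/3) = 15.6%, an excess of 0.6 points. The 95% half-width for one arm is 1.96 × √(0.15 × 0.85/90) = 7.4 points. For a difference between two arms it is 7.4 × √2, about 10.4 points.

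**Step 3: unequal elective rates.** Suppose both arms have s = 15%, but e is 15% in one and 7.5% in the other. The curves read 1 − 0.70^(1/2) = 16.3% and 15.6%, a spurious difference of 0.7 points.

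**Step 4: can the percentiles be estimated?** From the same simulation, counting events only to 34 weeks at 0.5:1, the share of runs in which each level is reached is:

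| True risk s | 25th percentile | Median | 75th percentile |
|---|---|---|---|
| 10% | 0% | 0% | 0% |
| 20% | 19% | 0% | 0% |
| 30% | 93% | 0.2% | 0% |
| 40% | about 100% | 23% | 0% |

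What counts is where the curve crosses, not the share of women with an event. At s = 23.5% and e = 11.75% the curve reads 1 − 0.6475^(2/3) = 25.2%, so the 25th percentile is reached with fewer than 25% of women having the event. The mean needs no such level. With the last times censored, however, it is a restricted mean, and no common cut-off is given.

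**Step 5: curve against primary proportion.** The protocol's proportion counts all spontaneous births before each limit, so it differs from the curve only through the censoring of elective births and any losses. The SAP's proportion counts only births after 32 but before 34 weeks, while its curve also counts earlier ones. That second mismatch is separate from the handling of elective deliveries.

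**The case against.** The strongest reply is that little depends on this. The SAP labels the analysis exploratory, the primary test is a CMH test on proportions, and with complete follow-up the crude proportion before 32 or 34 weeks already is the cumulative incidence. The excess is far below the sampling error in Step 2. The one-third elective share is not a trial figure. Trial women are selected for a short cervix or a previous preterm birth or membrane rupture, and protocol section 5.8 counts delivery after membrane rupture before labor as spontaneous; both suggest a smaller elective share. If spontaneous births up to 36 6/7 weeks count as events, more percentiles could be reached.

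All of this stands, and it limits the point. It does not make the estimator right for its stated target. Protocol section 9 also describes the curve in the paragraph on primary results, and SAP section 1 makes the protocol the final reference, so the curve's risks are likely to be read beside the proportions.

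A reader might go further and infer that the treatment comparison is biased, because the trial is open-label and indicated births could differ by arm. No passage says that they will, and even a doubling moves the arms apart by only 0.7 points in Step 3. A reader might also infer that the log-rank test is invalid. It remains a valid comparison of cause-specific hazards. Finally, that electively delivered women stay in the primary denominator as non-events is the natural reading of a proportion per group, but neither document states it.

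**Conclusion.** The concern holds in a limited form. Censoring elective deliveries gives a curve that overstates the risk of spontaneous birth by weeks 32 and 34 whenever some elective births precede spontaneous ones. At 0.5:1 the excess runs from 0.3 points at a true risk of 10% to 5.7 points at 40%; at 0.1:1 it is 0.2 points at 20% and 1.0 at 40%. These figures rest on assumed event rates, proportional hazards and a borrowed elective share, and are more likely too high than too low for this trial.

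The documents do not support saying that the percentiles cannot be estimated. If events count only to 34 weeks, the 75th percentile is in effect never reached, the median rarely, and the 25th only if the curve crosses 25%. Because the horizon is not stated, the correct statement is that they may not be estimable.

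The primary CMH test, the log-rank test and the sample size do not change.

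**What to change.** In SAP section 10, and in protocol section 9 at its next amendment:

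- Estimate the cumulative incidence of spontaneous birth by Aalen-Johansen on the gestational-age scale, with delayed entry at inclusion and elective delivery as a competing event.
- Report risks and risk differences with 95% confidence intervals at the protocol's limits (before 32 0/7 and before 34 0/7) in place of the quartiles and mean.
- State the gestational age at which events stop counting.
- Keep the log-rank test and describe it as the cause-specific comparison.
- State that electively delivered women count as non-events in the primary proportion, and say how the SAP's 32-to-34-week proportion relates to a curve that also counts earlier births.

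No new data are needed: protocol section 5.8 already requires record review to classify births before weeks 32 and 34 as indicated or spontaneous. The cost is a wording change and slightly more programming for delayed entry and the competing event. The new estimates should then agree with the protocol's proportions, apart from losses to follow-up and any deliveries before all women have entered.
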